#### 6.4 Assessing and Recording Adverse Events

Adverse events should be collected from the start of treatment through a minimum of 30 days following the last study treatment.

After informed consent has been obtained, and prior to initiation of investigational treatment, only serious adverse events caused by a protocol-mandated intervention should be reported (e.g., serious adverse events related to invasive procedures such as biopsies).

**After initiation of study treatment**, all adverse events will be reported according to the guidelines in the following sections. Throughout the study, investigators should report any deaths, serious adverse events, or other adverse events of concern that are believed to be related to the investigational intervention.

An adverse event is defined as any untoward medical occurrence in a patient or clinical investigation subject administered a pharmaceutical product and which does not necessarily have to have a causal relationship with this treatment. An adverse event can therefore be any unfavorable and unintended sign (including an abnormal laboratory finding, for example), symptom, or disease temporally associated with the use of a medicinal product or protocol-specified procedure, whether or not considered related to the medicinal product or protocol-specified procedure. Any worsening (i.e., any clinically significant adverse change in frequency and/or intensity) of a preexisting condition that is temporally associated with the use of pembrolizumab, is also an adverse event.

Adverse events may occur during the course of the use of Pembrolizumab in clinical trials or within the follow-up period specified by the protocol, or prescribed in clinical practice, from overdose (whether accidental or intentional), from abuse and from withdrawal.

Table 6. Adverse Event Reporting Overview						
Event Type	Collection Timeframe	Reporting Timeframe	Reference			
Routine Adverse Events	the start of treatment through at	Within 30 days to UVa	Section 6.4			
Serious Adverse Events†	least 30 days following the last study treatment	Within 24h to UVa	Section 6.4.4.1			
Events of Clinical Interest	the start of treatment through 90 days following the last dose of pembrolizumab (or date subject starts new cancer treatment)	Within 24h to UVa	Section 6.4.4.2			
Overdose	On pembrolizumab dosing days	Within 24h to UVa	Section 6.4.2			

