### 6.4.4 Immediate Reporting of Adverse Events to the Sponsor-Investigator

### 6.4.4.1 Serious Adverse Events

Any serious adverse event, or follow up to a serious adverse event, including death due to any cause other than progression of the cancer under study that occurs to any subject from the time of start of treatment through 30 days following the last dose of study treatment, or the initiation of new anticancer therapy, whichever is earlier, whether or not related to pembrolizumab, must be reported within 24 hours to the Sponsor-Investigator. Additionally, after informed consent has been obtained, and prior to start of treatment, serious adverse events determined to be caused by a protocol-mandated intervention should also be reported.

Non-serious Events of Clinical Interest (See Section 6.4.4.2) will be forwarded to Sponsor-Investigator and will be handled in the same manner as SAEs.

Additionally, any serious adverse event, considered by an investigator who is a qualified physician to be related to Pembrolizumab that is brought to the attention of the investigator at any time outside of the time period specified in the previous paragraph also must be reported immediately to the Sponsor-Investigator.

All subjects with serious adverse events must be followed up for outcome.

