## 6.4.4.2 Events of Clinical Interest

Selected non-serious and serious adverse events are also known as Events of Clinical Interest (ECI) and must be recorded as such on the Adverse Event case report forms/worksheets and reported within 24 hours to the Sponsor-Investigator using the Safety Reporting Form.

Events of clinical interest for this trial include:

1. an overdose of Pembrolizumab, as defined in Section 6.4.2 - Definition of an Overdose for This Protocol and Reporting of Overdose to the Sponsor-Investigator, that is not associated with clinical symptoms or abnormal laboratory results.

2. an elevated AST or ALT lab value that is greater than or equal to 3X the upper limit of normal and an elevated total bilirubin lab value that is greater than or equal to 2X the upper limit of normal and, at the same time, an alkaline phosphatase lab value that is less than 2X the upper limit of normal, as determined by way of protocol-specified laboratory testing or unscheduled laboratory testing.\*

\*Note: These criteria are based upon available regulatory guidance documents. The purpose of the criteria is to specify a threshold of abnormal hepatic tests that may require an additional evaluation for an underlying etiology. The trial site guidance for assessment and follow up of these criteria can be found in the Investigator Trial File Binder (or equivalent).

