#### 3. Additional adverse events:

A separate guidance document has been provided titled "Event of Clinical Interest Guidance Document" (previously entitled, "Event of Clinical Interest and Immune-Related Adverse Event Guidance Document"). This document provides guidance regarding identification, evaluation and management of ECIs and irAEs.

ECIs (both non-serious and serious adverse events) identified in this guidance document from the date of first dose through 90 days following cessation of treatment, or 30 days after the initiation of a new anticancer therapy, whichever is earlier, need to be reported within 24 hours to the Sponsor-Investigator using the Safety Reporting Form.

Subjects should be assessed for possible ECIs prior to each dose. Lab results should be evaluated and subjects should be asked for signs and symptoms suggestive of an immune-related event. Subjects who develop an ECI thought to be immune-related should have additional testing to rule out other etiologic causes. If lab results or symptoms indicate a possible immune-related ECI, then additional testing should be performed to rule out other etiologic causes. If no other cause is found, then it is assumed to be immune-related.

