### 6.4.4.3 UVA Cancer Center DSMC Reporting Requirements

All adverse events must be reported into the University of Virginia Cancer Center OnCore database within the time frame specified below:

	Grade 1	Gra	ade 2		Grade 3 Grade 4 & 5					
	Expected and	Expected	Unexpected	Expe	ected	Unexp	pected	Expected	Unexpected	
	unexpected		·	Without hospitalization	With hospitalization	Without hospitalization	With hospitalization		•	
Unrelated Unlikely	Not required	Not required	Not required	OnCore 30 days	OnCore 15 days	OnCore 30 days	OnCore 15 days	OnCore 15 days	OnCore 15 days	
Possible Probable Definite	OnCore 30 days	OnCore 30 days	OnCore 15 days	OnCore 30 days	OnCore 15 days	OnCore 15 days	OnCore 15 days	OnCore 15 days	OnCore (24-hrs)* 7 days	

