## 7.4 Safety and Futility Monitoring

## 7.4.1 Safety monitoring

Dose Limiting Toxicity (DLT) is defined as an adverse event which: i) is determined to be at least possibly related to treatment with pembrolizumab; ii) occurs within the first 30 days after the first pembrolizumab infusion; and iii) meets one of the below criteria:

- Pneumonitis Grade  $\geq$  3
- Any non-hematological toxicity Grade  $\geq$  3, except for the following:
  - Grade 3 toxicity that is expected from standard of care cisplatin and radiation
  - Grade 3 Colitis, hypophisitis, or hyperthyroidism lasting less than 7 days
  - Grade 3 electrolyte toxicities that are corrected to grade 1 or less within 24 hours
  - Grade 3 hypertension that can be controlled with oral medications and does not require treatment delay for > 7 days
  - Grade 3 diarrhea that is not refractory to anti diarrhea medications and is corrected to Grade 1 or less within 48 hours
  - Grade 3 nausea and vomiting that is not refractory to anti-emetic therapy and is corrected to Grade 1 or less within 48 hours
  - Grade 3 rise in creatinine, if corrected to Grade 2 or less after up to 2 liters of intravenous fluids within 24 hours
  - Grade 3 elevation in AST/ALT if < 1.5 times the baseline level
  - Grade 3 elevation of ALP (alkaline phosphatase)
  - Grade 3 hypoalbuminemia
  - o Grade 3 lymphopenia

- Grade 3 rash if it returns to ≤ grade 2 after 1 week of symptomatic treatment
- Any Grade ≥ 4 toxicity
- Other AEs if they are clearly related to pembrolizumab and are causing substantial morbidity for subjects, as determined by the study chair.

Within each arm, safety will be assessed by monitoring the number of patients who experience a DLT. Results reported in ASCO 2015 abstracts [22, 23] for pembrolizumab in combination with other treatments resulted in an overall DLT rate of 1/59=2% with a 90%Cl(1%, 8%). For this study the upper boundary of a sequential probability ratio test (SPRT) based upon a binomial test of proportions for DLT will be used for monitoring to protect against excessive failure rates. The stopping boundary is for a SPRT contrasting a 5% versus 25% DLT rate, with nominal type I and II errors of 10% and 10%, respectively. The slope of the parallel line for monitoring is 1.190 and the intercept is 0.128.

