Safety stopping guidelines for the occurrence of DLTs are detailed in the following table. If a stopping bound is crossed in either arm then accrual to the study will be suspended until the study PI, co-investigators and the DSMC can review the data, and determine if the study should continue, be amended or be closed to further accrual.

Incidence of treatment related DLTs	
Number of patients in an Arm	Stopping boundary
2-6	≥ 2
7-14	≥ 3
15-21	≥ 4
22-29	≥ 5
30-37	≥ 6
38-44	≥ 7

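### Dose-limiting toxicities have no reporting line of their own, so one that is neither serious nor an event of clinical interest may take up to 15 days, or in one case 30, to enter a stopping count that runs patient by patient

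*Combined protocol and SAP*

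**What the plan says.** **Reporting clocks.** Table 6 in Section 6.4 sets the deadline by type of event. Routine adverse events are due "Within 30 days to UVa". Serious adverse events (SAEs), ECIs, overdose and pregnancy each have a 24-hour line. DLTs have none.

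- Section 6.4.4.1 covers SAEs, which, "whether or not related to pembrolizumab, must be reported within 24 hours to the Sponsor-Investigator".
- Section 6.4.4.2 covers ECIs, serious or not. Those identified in a separate guidance document "need to be reported within 24 hours to the Sponsor-Investigator using the Safety Reporting Form". For a possible immune-related ECI the default attribution is: "If no other cause is found, then it is assumed to be immune-related".
- Section 6.4.4.3 sets OnCore deadlines by grade, expectedness, relatedness and hospitalization. For a related Grade 3 event that is expected and not hospitalised the entry is "OnCore 30 days".

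**Stopping rule.** Section 7.4.1 defines a DLT by grade, by at least possible relation to pembrolizumab, and by onset within 30 days of the first infusion. It then states: "Within each arm, safety will be assessed by monitoring the number of patients who experience a DLT". The table starts at 2 DLTs in 2 to 6 patients, and "If a stopping bound is crossed in either arm then accrual to the study will be suspended" pending review. The section gives no deadline for reporting a DLT, names no role to keep the count, and does not say which patients make up the number in the arm.

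**The concern.** A sequential boundary works only as fast as the events reach whoever keeps the count. The study is multi-center, so UVa can count only what sites have sent. A DLT is defined by grade and relatedness, whereas the 24-hour lines are triggered by seriousness or ECI status. The two sets overlap but are not the same. A Grade 3 rash that persists beyond a week, or an expected Grade 4 laboratory toxicity managed without admission, can be a DLT without clearly being an SAE or one of the ECIs listed in the protocol text.

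Two details add to this. Table 7 treats anything in the Investigator's Brochure as expected for expedited reporting, so recognised toxicities of the drug get the slower OnCore clocks. The last DLT criterion is a judgement by the study chair, who cannot make it before the event is reported.

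At stake is the number of patients who enter an arm after the data have crossed the boundary but before anyone can see it. In Arm 2 each of them starts pembrolizumab on Day 1.

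**Working it through.** **1. The plan's boundary.** Inputs from 7.4.1: DLT rates 5% and 25%, type I and II errors of 10% each.

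- D = ln[(0.25 × 0.95)/(0.05 × 0.75)] = ln 6.333 = 1.846
- Intercept = ln(0.90/0.10)/D = 2.197/1.846 = 1.190
- Slope = ln(0.95/0.75)/D = 0.236/1.846 = 0.128
- Boundary = 1.190 + 0.128n, rounded up. n = 6 gives 1.96, so 2; n = 7 gives 2.09, so 3; n = 44 gives 6.83, so 7.

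All six rows of the table reproduce. (The text of 7.4.1 attaches the words slope and intercept to the wrong constants. That is a separate point and does not affect the table.) The exact probability of crossing by 44 patients is 6.3% at a 5% DLT rate and 97.1% at 25%.

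**2. Which clock a DLT gets.** By definition it sits in the related row of the 6.4.4.3 table.

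| DLT | Earliest binding deadline |
|---|---|
| Serious, any grade | 24 hours (6.4.4.1) |
| ECI, serious or not | 24 hours (6.4.4.2) |
| Neither; Grade 4, unexpected | OnCore 24 hours / 7 days |
| Neither; Grade 4, expected | OnCore 15 days |
| Neither; Grade 3, unexpected, no hospitalization | OnCore 15 days |
| Neither; Grade 3, expected, no hospitalization | 30 days (OnCore and Table 6) |

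OnCore is UVa's own database, so I take its deadline as the binding one where it is shorter than Table 6.

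**3. Lag in patients.** Section 7.2 expects 4 patients a month, about 2 per arm. With a 30.44-day month, an arm enrols 2 × 30/30.44 = 1.97 patients in 30 days, 0.99 in 15 days and 0.07 in one day. Compared with 24-hour reporting, the lag alone costs about 1.9 or 0.9 patients per arm.

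**4. Simulated number of patients at suspension.** Assumptions: DLT onset uniform over 30 days, each report arriving on its last permitted day, up to 44 patients per arm. The denominator is not defined, so two readings were run.

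*(a) Patients started by the date of DLT onset*, even accrual, 25% DLT rate, 20,000 runs. In Arm 2 the mean is 11.97 with a 1-day lag, 12.74 with 15 days and 13.87 with 30 days: 0.8 and 1.9 extra. In Arm 1, with first infusion assumed at day 56, it is 15.6 with 1 day and 17.5 with 30 days: again 1.9 extra.

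*(b) Patients started by the date the report arrives*, Arm 2, exponential gaps between patients, runs that never cross counted as 44. Ranges are over repeated simulations of 3,000 to 200,000 runs.

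| Reporting | 25% DLT rate | 40% DLT rate | Extra patients |
|---|---|---|---|
| All within 24 hours | 13.7 to 14.0 | 6.9 to 7.0 | – |
| All at 15 days | 15.3 to 15.4 | 8.2 | 1.2 to 1.6 |
| Half at 24 hours, half at 30 days | 15.1 to 15.4 | 8.1 to 8.3 | 1.1 to 1.7 |
| All at 30 days | 17.1 to 17.4 | 9.5 to 9.7 | 2.5 to 3.4 |

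Reading (b) exceeds the pure lag because a late DLT is compared with a larger patient count: 2 DLTs cross at 6 patients but not at 8. The probability of ever crossing hardly moves (96.7% with 24-hour and 96.2% with 30-day reporting at a 25% rate).

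**The case against.** A reader might infer that every non-serious DLT waits 30 days and that the boundary therefore runs a month behind. The documents do not support that.

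- Non-serious ECIs already go in within 24 hours. Every DLT is at least possibly related to pembrolizumab, and a possible immune-related ECI with no other cause found is treated as immune-related, so the overlap may be large.
- Seriousness includes other important medical events. Table 7 describes Grade 3 as severe or medically significant and Grade 4 as life-threatening in its consequences, so many DLTs will be SAEs.
- Among related events of Grade 3 or above, only one OnCore cell allows 30 days, and 7.4.1 narrows it by exempting Grade 3 toxicity expected from cisplatin and radiation.
- Deadlines are limits. Having every report arrive on the last day gives a ceiling, not an estimate.
- The comparison with a later, higher row depends on a denominator that 7.4.1 does not state.
- Under Section 6.4.5.1 the DSMC reviews all adverse events and the application of stopping rules every month.

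All of this limits the size of the problem, and the first five points stand in full. The last helps less: the DSMC cannot count a DLT that has not been reported, and a monthly meeting can add to the delay. None of the points supplies a clock that covers every DLT.

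**Conclusion.** The gap is real but modest. DLTs have no reporting line of their own. One that is neither serious nor an ECI may take up to 15 days to reach UVa through OnCore if it is Grade 3, unexpected and without hospitalization, or Grade 4 and expected. It may take up to 30 days if it is Grade 3, expected and without hospitalization. How many DLTs fall there cannot be determined without the ECI guidance document.

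For Arm 2, the cost is about 1 to 1.5 extra patients before suspension with a 15-day lag or with half of DLTs already expedited (single scenarios run from 0.8 to 1.7). It is at most about 2 to 3 (1.9 to 3.4) if every DLT takes 30 days. These figures rest on 2 patients a month per arm, uniform onset, last-day reporting, and true DLT rates of 25% or 40%. They do not show that the rule would miss an unsafe arm, since it is crossed almost as often but later. The change is worth making because it is nearly free and protects the one numerical safety rule in the plan.

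**What to change.** 1. Add a row to Table 6: a DLT as defined in 7.4.1 is reported to UVa within 24 hours of awareness, regardless of seriousness or expectedness.
2. Put the same exception in the Section 6.4.4.3 table, so that the two sets of deadlines agree.
3. State in 7.4.1 that the count for each arm is updated and checked against the boundary on receipt of each DLT report, name the role that does it, and say which patients form the denominator.

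The cost is one table row, one exception and a sentence or two, plus a few extra 24-hour forms: 0.05 × 44 = 2.2 DLTs per arm at a 5% rate, some of which would be expedited anyway. The DLT definition, the boundary and the treatment rules do not change.

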## 6.4.1 Assessment of Adverse Events

All adverse events, whether reported by the subject or noted by study personnel, should be recorded in the subject's medical record. Adverse events should be assessed for seriousness, severity, attribute and expectedness, in relation to Pembrolizumab treatment, by the Principal Investigator or designee. The following sections provide definitions for adverse event characteristics and reporting requirements.

# 6.4.1.1 Expectedness

The expectedness of the adverse event will be determined by the Investigator based on current literature, the Investigator's Brochure or package insert and the Investigator's experience. Adverse events commonly observed with the standard of care chemoradiation treatment, such as hematological, genitourinary and gastrointestinal, should be expected during the CRT interval.

## 6.4.1.2 Severity

The descriptions and grading scales found in the revised NCI Common Terminology Criteria for Adverse Events (CTCAE) version 4.03 will be utilized for AE reporting. All appropriate treatment areas should have access to a copy of the CTCAE version 4.03. A copy of the CTCAE version 4.03 can be downloaded from the CTEP web site (http://ctep.cancer.gov).

## 6.4.1.3 Attribution

The Principal Investigator will evaluate all AEs and assess their toxicity and attribution, if any, to pembrolizumab. See Table 8 for further guidance on evaluation of attribute. The following criteria will define the attribution:

**Definite:** The AE is clearly related to the investigational intervention. **Probable:** The AE is likely related to the investigational intervention. **Possible:** The AE may be related to the investigational intervention. **Unlikely**: The AE is doubtfully related to the investigational intervention. **Unrelated**: The AE is NOT related to the investigational intervention.

## 6.4.1.4 Seriousness

A serious adverse event is any adverse event that:

- Results in death;
- Is life threatening;
- Results in persistent or significant disability/incapacity;
- Results in or prolongs an existing inpatient hospitalization;
- Is a congenital anomaly/birth defect;
- Is a new cancer (that is not a condition of the study);
- Is associated with an overdose;
- Is another important medical event

\*Hospitalization or prolonged hospitalization should be documented and reported as a serious adverse event, except if the hospitalization meets at least one of the following criteria:

- The hospitalization is less than 24 hours without an admission
- Hospitalization for respite care
- Planned hospitalization required by the protocol (e.g., for anticipated or protocol specified procedures such as administration of Intravenous fluids, central line insertion, biopsy procedures )
- Hospitalization for a preexisting condition, provided that all of the following criteria are met:
  - The hospitalization was planned prior to the study or was scheduled during the study when elective surgery became necessary because of the expected normal progression of the disease.
  - The subject has not suffered an adverse event.

If the hospitalization meets any of these criteria, then it is not considered a serious adverse event.

Refer to Table 7 for additional details regarding each of the above criteria.

### 6.4.2 Definition of an Overdose

For purposes of this trial, an overdose will be defined as any dose exceeding the prescribed dose for pembrolizumab by 20% over the prescribed dose. No specific information is available on the treatment of overdose of pembrolizumab. In the event of overdose, pembrolizumab should be discontinued and the subject should be observed closely for signs of toxicity. Appropriate supportive treatment should be provided if clinically indicated.

If an adverse event(s) is associated with ("results from") the overdose of a Pembrolizumab, the adverse event(s) is reported as a serious adverse event, even if no other seriousness criteria are met.

If a dose of pembrolizumab meeting the protocol definition of overdose is taken without any associated clinical symptoms or abnormal laboratory results, the overdose is reported as a non-serious Event of Clinical Interest (ECI), using the terminology "accidental or intentional overdose without adverse effect."

All reports of overdose with and without an adverse event must be reported within 24 hours to the Sponsor-Investigator (Fax notification to UVa) using the Safety Reporting Form.

## 6.4.3 Reporting of Pregnancy and Lactation to the Sponsor-Investigator

Although pregnancy and lactation are not considered adverse events, it is the responsibility of investigators or their designees to report any pregnancy or lactation in a subject (spontaneously reported to them) that occurs during the trial or within 120 days of completing the pembrolizumab treatment, or 30 days following cessation of pembrolizumab treatment if the subject initiates new anticancer therapy, whichever is earlier. All subjects who become pregnant must be followed to the completion/termination of the pregnancy. Pregnancy outcomes of spontaneous abortion, missed abortion, benign hydatidiform mole, blighted ovum, fetal death, intrauterine death, miscarriage and stillbirth must be reported as serious events (Important Medical Events). If the pregnancy continues to term, the outcome (health of infant) must also be reported.

Such events must be reported within 24 hours to the Sponsor-Investigator using the Safety Reporting Form.

